1.0 Hypothesis and Objectives

1.1 Specific hypotheses:

- 1.1.1 Low serum 25(OH)D will be associated with increased treatment-related morbidity.
- 1.1.2 Repletion of 25(OH)D will be associated with an increase towards normal of serum leptin levels.
- 1.1.3 VDR *FokI* SNP polymorphism will be associated with lower circulating levels of 25(OH)D.

1.2 Objective(s)

1.2.1 Primary objective:

1.2.1.1 To assess treatment-related morbidity (including 30-day postoperative surgical morbidity and chemotherapy-related morbidity) and 1-year disease-free survival in patients with deficient serum 25(OH)D levels at the time of ovarian, primary peritoneal, or fallopian tube cancer diagnosis who did and did not receive vitamin D repletion.

1.2.2 Secondary objectives:

1.2.2.1 To describe serum 25(OH)D levels, serum leptin levels, and VDR *FokI* SNP status among newly diagnosed ovarian, primary peritoneal, or fallopian tube cancer patients.

1.2.2.2 To determine the proportion of patients with ovarian, primary peritoneal, or fallopian tube cancer that have deficient vitamin D at diagnosis and have normal serum 25(OH)D after oral vitamin D supplementation during primary therapy.

1.2.2.3 To identify potential relationships between serum 25(OH)D and serum leptin levels when controlling for BMI.

1.2.2.4 To evaluate change of serum leptin levels with repletion of 25(OH)D in patients with low levels at the time of ovarian primary peritoneal, or fallopian tube cancer diagnosis.

1.3 Translational Research Objectives:

1.3.1 To evaluate VDR *FokI* SNP status relationship with serum 25(OH)D levels and treatment-related morbidity and cancer outcomes.

2.0 Background Information. Rationale for selected approach and

trial design.

2.1 Overview of Ovarian Cancer

Ovarian cancer (including primary peritoneal and fallopian tube cancer) is the fifth leading cause of cancer-related deaths in women in the United States and the most lethal gynecologic cancer [1]. It was estimated that in 2016, more than 22,000 women will be diagnosed with ovarian cancer leading to more than 14,000 deaths [2]. The median age of diagnosis of women with ovarian cancer is 63, with increased comorbidities leading to treatment-related toxicities in older women [3]. The inability to receive adjuvant chemotherapy negatively impacts overall survival (OS). Number of cycles of chemotherapy also appears to be important. For example, elderly women who receive more than three chemotherapy cycles have been found to have improved OS [3]. Further study to identify factors to improve treatment tolerability and reduce treatment-related morbidity in ovarian cancer patients are warranted.

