Vitamin D therapy will be stopped in any patient developing the above exclusion criteria of GFR <30, inability to tolerate oral medications, malabsorption syndrome, or primary hyperparathyroidism. In the unlikely event of evidence of vitamin D toxicity, treatment with vitamin D will be stopped. The Stephenson Cancer Center laboratory defines vitamin D toxicity as levels >100 ng/mL. Based on IOM literature, it would highly unlikely for individuals to experience vitamin D toxicity at the prescribed doses. Symptoms of vitamin D intoxication are caused by the resultant hypercalcemia and include anorexia, weight loss, polyuria, arrhythmias, fatigue, and soft tissue calcifications [20]. Patients experiencing these symptoms would receive testing for serum calcium and vitamin D. Vitamin D treatment would be stopped for any value indicative of toxicity.

Demographic, clinical, and disease characteristics and outcomes will be collected from all patients prospectively. The patient's treatment course information will also be collected prospectively, but will not be dictated by this study. Serum 25(OH)D and leptin levels will be collected again at the completion of primary therapy, 6 months after the completion of primary therapy, and at the time of disease recurrence. If disease recurrence occurs prior to 6 months after completion of primary therapy, this time point will be omitted. If disease recurrence does not occur prior to 1 year, serum 25(OH)D and leptin levels will be drawn at the time of the 1-year surveillance visit. If patients remain vitamin D deficient at any of these follow-up time points, they will be referred to an endocrinologist or primary care physician for further work-up and treatment of their vitamin D deficiency. Patients who are vitamin D deficient at completion of therapy but were not previously on supplement will be

IRB NUMBER: 7488
IRB APPROVAL DATE: 11/23/2021

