referred to a primary care physician for further management. Data collection will continue for 1 year or until the time of disease recurrence. Patient's will no longer have data collected after obtaining serum 25(OH)D and leptin levels at the time of recurrence. A retrospective cohort of women with low serum 25(OH)D that did not receive repletion of vitamin D will be used as a control group for comparison. This control group will be identified from available tumor bank serum samples including those previously identified in the above-mentioned unpublished study at the University of Oklahoma. These samples will be used to evaluate serum levels of 25(OH)D, leptin, and evaluate Buffycots VDR SNP polymorphism for *FokI*.

Cohort	Therapy
1 (Normal 25(OH)D)	None
2 (Low 25(OH)D (<20ng/mL)	50,000 IU cholecalciferol weekly for 8 weeks followed by 2,000 IU daily thereafter

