4.0 Study Population

4.1 Eligible Patients

4.1.1 The study population will consist of women with newly diagnosed ovarian, fallopian tube, or primary peritoneal cancer and no previous treatment.

4.1.2 A retrospective cohort of women with ovarian, fallopian tube, or primary peritoneal cancer and low serum 25(OH)D that did not receive repletion identified from available tumor bank serum samples.

IRB NUMBER: 7488
IRB APPROVAL DATE: 11/23/2021

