4.2 Inclusion Criteria (Prospective patients)

4.2.1 Patients must have a histologic diagnosis of ovarian, fallopian tube, or primary peritoneal carcinoma per pre-treatment biopsies by laparoscopy, or interventional radiology, paracentesis, or CT guided core biopsy. Histologic documentation of the original primary tumor is required via the pathology report.

4.2.2 Patients must have adequate:

4.2.2.1 Renal function: Glomerular Filtration Rate (GFR) ≥ 30 .

4.2.2.2 Gastrointestinal absorption: No underlying malabsorption syndrome (i.e. inflammatory bowel disease, celiac disease).

4.2.2.3 Ability to tolerate oral medication.

4.2.3 Patients taking vitamin D at the time of enrollment without a diagnosis of vitamin D deficiency.

4.2.4 Patients of childbearing potential must have a negative pregnancy test prior to the study entry and be practicing an effective form of contraception. If applicable, patients must discontinue breastfeeding prior to study entry.

4.2.5 Patients must have signed an IRB-approved informed consent and authorization permitting release of personal health information.

4.2.6 Patients must be at least 18 years old.

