12.0 Statistical Methods

Upon analysis, patients will be divided into two groups: Vitamin D Deficient Women and Vitamin D Normal Women.

IRB NUMBER: 7488
IRB APPROVAL DATE: 11/23/2021

Outcomes to be analyzed include differences in demographics, clinical, and tumor characteristics between groups, and differences in treatment-related morbidity or mortality between groups, including completion of treatment and treatment delays, and survival. Both 30-day postoperative surgical morbidity and chemotherapy-related morbidity will be assessed. The ability to normalize 25(OH)D levels with oral supplementation in the vitamin D deficient group will be evaluated.

Descriptive statistics will be used to summarize the demographic and clinical characteristics of patients. Chi-square and t-tests will be used to make comparisons between groups. Survival will be estimated with Kaplan-Meier curves and Cox proportional hazards regression. The anticipated enrollment is 100 patients based on estimated new diagnoses of ovarian cancer treated in the Division of Gynecologic Oncology annually at the Stephenson Cancer Center. Based on the previously mentioned unpublished data, we presume that at least 25 of the prospectively enrolled patients will be vitamin D deficient. All of the vitamin D deficient women will be repleted with oral vitamin D. We will compare outcomes between these patients and 75 vitamin D deficient ovarian cancer patients from previous years (these will include patients from the above-mentioned previous retrospective review as well as other patients with banked blood samples) using logistic regression. We will control for age, stage, and histology. With 25 prospective patients and 75 retrospective patients we will have 80% power to detect differences of 32% in chemotherapy delay between ovarian patients who were not vitamin D deficient (33%) and who were vitamin D deficient (65%).

Additionally, the association between serum leptin and 25(OH)D levels will be compared among groups, including any change in leptin levels observed in the vitamin D supplementation group. Because there is a positive linear association between BMI and serum leptin levels, BMI will be corrected for during analysis for potential relationships between serum leptin and 25(OH)D.

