#### 6. Antitumor Evaluation

1. Treatment related morbidity (including 30-day postoperative surgical morbidity and chemotherapy-related morbidity) will be summarized by descriptive statistics as appropriate and compared across groups (chi-square for categorical variable).
2. Progression-Free Survival (PFS) at end of study (EOS) is defined as the time in months from first dose of the drug to the date of death or the first documented date of progression, whichever comes first. For patients who did not die and did not have progression, the PFS is censored at the last documented tumor assessment.

Survival curve for PFS will be generated using the Kaplan-Meier method. Median PFS with 95% CI will be computed.

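### The non-randomised repleted-versus-unrepleted comparison adjusts only for age, stage and histology, and leaves out the comorbidity that the protocol itself links to treatment toxicity

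*Protocol*

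**What the plan says.** Protocol 1.2 sets the primary objective: morbidity and 1-year disease-free survival in deficient women "who did and did not receive vitamin D repletion". Nobody is randomised. Protocol 3.0 states: "A retrospective cohort of women with low serum 25(OH)D that did not receive repletion of vitamin D will be used as a control group". Protocol 4.1 defines those controls by cancer type and "low serum 25(OH)D that did not receive repletion identified from available tumor bank serum samples".

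Protocol 12.0 compares about 25 repleted women with 75 controls by logistic regression and lists the covariates: "We will control for age, stage, and histology". SAP 2b repeats that sentence. Neither document names comorbidity, performance status or another fitness measure as a covariate, and neither plans matching, weighting or a sensitivity analysis for confounding.

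SAP section 6, item 1, where the morbidity analysis is specified, does not carry the model forward. Morbidity is described and "compared across groups (chi-square for categorical variable". Protocol 12.0 also plans Cox regression for survival but gives it no separate covariate list. SAP section 6, item 2, has only a Kaplan-Meier curve and median PFS.

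Protocol 2.1 describes the disease at older ages "with increased comorbidities leading to treatment-related toxicities in older women".

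**The concern.** In a non-randomised comparison, a cause of the outcome that differs between the groups and is left out of the model is credited to the treatment. The protocol names comorbidity as such a cause and then omits it.

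The groups also enter by different routes. Prospective women consent before treatment and, under section 4.2, need a GFR of at least 30, no malabsorption syndrome and the ability to take oral medication. Section 4.2 is headed as applying to prospective patients, and no such criterion is stated for controls. Some controls come from an earlier study of women aged 65 and older (Protocol 2.2, 3.0 and 12.0), whereas prospective women need only be 18. Applying the same exclusions to controls would remove the extremes and leave ordinary comorbidity unadjusted.

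At stake is whether a lower delay rate in repleted women can be attributed to vitamin D.

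**Working it through.** **1. The plan's own figure.** Inputs from Protocol 12.0: 25 v 75 women, delay 33% v 65%. The plan states no significance level; two-sided 5% is assumed.

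- Pooled rate = (25 × 0.33 + 75 × 0.65) / 100 = 0.57.
- Standard error under no difference = √[0.57 × 0.43 × (1/25 + 1/75)] = 0.1143.
- Standard error under the alternative = √[0.33 × 0.67/25 + 0.65 × 0.35/75] = 0.1090.
- z = (0.32 − 1.96 × 0.1143) / 0.1090 = 0.88, so power = 81%.

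The stated 80% reproduces. It is an unadjusted figure with no allowance for covariates or confounding.

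**2. Crude bias if comorbidity is ignored and vitamin D does nothing.** The documents give no comorbidity data, so the prevalences and odds ratios are assumptions. The control delay rate is held at the plan's 65%. Let r0 and r1 be the delay risks without and with comorbidity, linked by the odds ratio, and let pC and pR be the prevalences in controls and repleted women.

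- Solve (1 − pC) × r0 + pC × r1 = 0.65 for r0.
- Spurious difference = (pC − pR) × (r1 − r0).

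| Odds ratio | pC v pR | r0, r1 | Repleted rate | Spurious difference | Spurious odds ratio |
|---|---|---|---|---|---|
| 2 | 50% v 40% | 0.572, 0.728 | 63.4% | 1.6 points | 0.93 |
| 3 | 60% v 40% | 0.500, 0.750 | 60.0% | 5.0 points | 0.81 |
| 4 | 60% v 30% | 0.463, 0.775 | 55.6% | 9.4 points | 0.68 |
| any | equal | – | 65.0% | 0 | 1.00 |
| 2 | 40% v 50% | 0.589, 0.741 | 66.5% | −1.5 points (apparent harm) | 1.07 |

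Across the 12 combinations of pC 50% or 60%, pR 30% or 40%, and odds ratio 2, 3 or 4, the difference is 6.0 points or less in nine.

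**3. Effect on the test.** Exact enumeration of an uncorrected chi-square at 25 v 75, with 65% delay in controls, gives the chance of a significant result favouring repletion: 2.8% if the repleted rate is 65%, 7.2% at 60%, and 13.3% at 56% (close to the largest scenario). These are crude figures; adjusting for age would remove part of the excess.

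**4. What the model can carry.** The limiting count is non-delays.

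- Planning rates: 25 × 0.67 + 75 × 0.35 = 43. This takes 33% as the repleted rate, although Protocol 12.0 attaches it to women who were not deficient.
- No vitamin D effect: 100 × 0.35 = 35.
- Group (1), age (1), stage I-IV (3) and histology (at least 2) make 7 parameters, so 43/7 = 6.1 or 35/7 = 5.0 non-delays each, before any addition.
- With stage and histology cut to two categories each and comorbidity added: 5 parameters, so 8.6 or 7.0 each.

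**5. Power after adjustment.** If all covariates together explain a share R² of group membership, scale both group sizes by (1 − R²). Power falls from 81% to 79% (R² = 0.05), 77% (0.10), 72% (0.20) or 66% (0.30).

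**The case against.** The strongest reply is that the sentence in Protocol 2.1 is background about older women, and age is already in the model. The documented difference in case mix, a control source aged 65 and older, is also an age difference. The renal, absorption and oral-medication criteria are an eligibility matter. That leaves consent against tumor-bank entry, and the documents do not say who enters the bank. The size rests on assumed inputs, and the model is already thin.

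Much of this stands. A reader might infer three stronger things that the documents do not support:

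- *That the repleted women are healthier, so the bias favours repletion.* This is plausible from the entry routes, but no comorbidity data are given for either group.
- *That the bias could produce the planned effect.* The largest scenario is 9.4 points, under a third of 32 (9.4/32 = 0.29).
- *That the logistic model is the plan's only adjusted analysis.* A BMI-corrected leptin analysis and a Cox regression are also planned. Neither addresses morbidity.

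What does not stand is that age is enough. Age is a proxy, and women of the same age differ in comorbidity. In addition, if SAP section 6 is followed as written, the morbidity comparison is not adjusted even for age.

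**Conclusion.** The point holds as an omitted confounder of modest, uncertain size. The primary comparison is non-randomised, its covariate list stops at age, stage and histology, and the SAP's morbidity item has no covariates. Residual comorbidity can shift the estimate by roughly 2 to 9 points before age adjustment under the stated assumptions, in a direction the documents do not settle. That could turn a small or null effect into an apparent benefit, or mask a real one. The change should be made before analysis, because a covariate added once results are known would look data-driven.

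**What to change.** - **Covariates.** In Protocol 12.0 and SAP 2b, extend the list to age, stage, histology and pre-treatment comorbidity.
- **Measure.** Define comorbidity as one prespecified count of listed conditions, excluding the index cancer. Abstract it with the same form, from the last history and physical before first cancer treatment, in both groups.
- **SAP section 6, item 1.** Replace the chi-square with the adjusted logistic model as the morbidity analysis, and keep the chi-square as descriptive only.
- **Survival.** Use the same covariates in the Cox model of Protocol 12.0 and add that model to SAP section 6, item 2.
- **Sparse data.** Prespecify Firth penalised logistic regression from the outset, with stage and histology collapsed to a few named categories, because only about 35 to 43 non-delays are expected.

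**Cost.** One more parameter and one more chart item. Prospective women have a screening history and physical (Protocol 8.1), and Protocol 3.0 already says "Demographic, clinical, and disease characteristics and outcomes will be collected from all patients prospectively". For controls, records must be consulted anyway for stage, histology and delay. SAP section 9 rules out imputation, so a control with no usable pre-treatment history would drop out of the model; the form should state how unrecorded conditions are counted. Power falls from 81% to about 77-79% if all covariates explain 5-10% of group membership, and further if they explain more. Part of that loss comes from the three covariates already planned.

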2.2 Vitamin D Deficiency in Cancer

Vitamin D has been well-studied due to its role in many important cellular pathways. Laboratory and observational studies suggest that it plays a role in many diseases such as autoimmune diseases, cardiovascular disease, diabetes, cancer risk and cancer survival. The correlation of low serum 25(OH)D with elevated risk for malignancy has been best studied in colorectal cancer [4]. Decreased levels of serum 25(OH)D have been correlated with increased risk of breast cancer in postmenopausal women. [5]. Women receiving chemotherapy and anti-hormonal therapy for breast cancer experience treatment-induced bone loss due to premature ovarian failure or direct cytotoxic effects of chemotherapy. This causes an increase in the osteoporosis and skeletal morbidity risk [6]. Similar effects can be estimated in ovarian cancer patients given that standard treatment requires surgical menopause as well as cytotoxic therapy in the majority of patients.

The majority of studies pertaining to vitamin D and ovarian cancer concern the association of low serum 25(OH)D with increased cancer risk. Limited study has been performed investigating the correlation of serum vitamin D and ovarian cancer prognosis or treatment-related morbidity. A study performed in Australia investigated serum 25(OH)D levels at the time of diagnosis of ovarian cancer in 670 women. They noted a significant association between higher circulating 25(OH)D concentrations and longer survival in women with ovarian cancer when adjusting for other clinical predictors of

survival [7]. Similarly, Walentowicz-Sadlecka et al. reported low serum 25(OH)D concentrations in women with ovarian cancer undergoing primary cytoreductive surgery to be associated with lower overall survival[8]. The impact of repletion of vitamin D in ovarian, primary peritoneal, or fallopian tube cancer patients has yet to be determined.

Findings from an unpublished study performed at the University of Oklahoma have shown an inverse correlation between low levels of serum vitamin D and treatment-related morbidity in women aged 65 years and older with ovarian cancer. More specifically, when comparing median serum 25(OH)D levels between patients who experienced chemotherapy delay ≥ 7 days versus those who did not, lower mean 25(OH)D levels were significantly associated with chemotherapy delays (23.6 ng/dL, n=28 no delay versus 14.6 ng/dL, n=30 delay, p=.0112). (Figure 1)[9].

[figure not shown]

Figure 1. Serum 25(OH)D levels by chemotherapy delay status. Delay (≥ 7 days) n=30, median 25(OH)D 14.6 ng/dL. No delay n=28, median 25(OH)D 23.6 ng/dL (p=0.0112).

To date, there have been no prospective or randomized controlled trials evaluating serum 25(OH)D and treatment-related risks in cancer patients. No data exists regarding the effect of repletion of vitamin D and prevention of ovarian cancer treatment-related morbidity. As previously mentioned, number of cycles of chemotherapy received appears to correlate with improved OS in women with ovarian cancer [3]. Given the findings of the above-mentioned study correlating low serum 25(OH)D levels and chemotherapy

delay, vitamin D represents a potentially modifiable factor that could improve treatment tolerance among women with ovarian cancer.

2.3 Leptin and Ovarian Cancer

Leptin is an adipokine that appears to stimulate growth of cancer cells while decreasing apoptosis [10]. Serum leptin levels have also been linked to elevated levels of pro-inflammatory cytokines in malignancy [11]. Retrospective analysis of data from NHANES III revealed an inverse relationship between serum leptin levels and cancer death in women [12]. In ovarian cancer, there is some data to show that lower leptin levels may be associated with increased initial tumor burden and subsequent increases in leptin may correlate with complete cytoreduction [13]. Further study is needed to better understand the role of leptin in ovarian cancer. Vitamin D receptors are involved in production of adipokines such as leptin; however, the response of serum leptin levels to repletion of vitamin D remains unclear [1]. Conflicting data exists between meta-analyses investigating changes in leptin following correction of vitamin D levels in humans [1]. This study aims to assess for potential relationships between serum 25(OH)D levels and leptin levels, including any changes that may occur during repletion of 25(OH)D.

Women with treatment-related morbidity often experience delays in treatment, changes in chemotherapeutic regimens and surgical or chemotherapy-related complications requiring hospitalization. Identifying modifiable risk factors among patients with ovarian cancer (including fallopian tube and primary peritoneal cancer) that can prevent treatment-related morbidity represents an important goal in the care of these women.

Safety:

Cholecalciferol is a generally safe and well-tolerated medication. Repletion of vitamin D is considered standard of care and will be undertaken utilizing current available guidelines [14].

Translational Research Background:

Vitamin D receptors (VDR) are extensively expressed in epithelial cells of both normal and tumor ovarian tissue. VDR functions as a transcriptional regulatory factor involved in decreasing cell proliferation and inhibition of apoptosis [15]. As such, this may carry implications for ovarian cancer tumorigenesis. The VDR rs2228570 (*FokI*) single nucleotide polymorphism (SNP) represents the most common and best studied SNP in the VDR gene leading to an alteration of VDR protein structure and decreased transcriptional activity as compared to the wild type [15, 16]. Meta-analyses of several small studies have associated *FokI* SNP with increased risk of ovarian cancer, [15, 16]. One such study performed a meta-analysis with pooled odds ratios and 95% confidence intervals to assess the associations between VDR polymorphisms (*Cdx-2*, *FokI*, *BsmI*, *ApaI*, and *TaqI*) and risk for breast and ovarian cancer. Only the *FokI* SNP was found to be associated with increased risk of breast and ovarian cancers [17]. Currently, no data exists to correlate VDR SNP polymorphisms to circulating 25(OH)D levels at the time of diagnosis of ovarian cancer. There is limited data to suggest that in both prostate cancer and colorectal cancer, the homozygous VDR *FokI* SNP (prostate) and homozygous VDR *TaqI* SNP (colorectal) are associated both with increased risk of the respective malignancy and lower circulating 25(OH)D levels [18, 19].

